6.7.1. Aberrant Behavior Checklist-Community (ABC-C)

The ABC-C instrument is a scale for rating inappropriate and maladaptive behavior of people with developmental disabilities, including intellectual disability and autism spectrum disorder (ASD), (Aman & Singh, 2017). Change and percent change from Baseline to Weeks 6, 14, 22, 30 and 38/ET in the ABC-C subscales of Irritability, Social Withdrawal, Stereotypic Behavior, Hyperactivity Noncompliance, and Inappropriate Speech will be calculated. In addition, a t-test will be used to test if within treatment changes from baseline are different from 0. Responder analyses (25% and 35% improvement) from baseline to each visit in each subscale will be calculated.

The Aberrant Behavior Checklist - Community, 2nd Edition, is completed at Screening, Visit 2, Visit 3, Visit 4, Visit 5, Visit 6, and Visit 7 EOS/ET. The ABC-C asks responders to rate behaviors from “0 - not at all a problem” to “3 - the problem is severe in degree” across 58 questions. ABC consists of five subscales as follows:

Table 6: ABC-C Subscale Scoring

Subscale Number	Subscale Name	Total Score for Response to Questions	Range
I	Irritability	2, 4, 8, 10, 14, 19, 25, 29, 34, 36, 41, 47, 50, 52, 57	0 to 45
II	Social Withdrawal	3, 5, 12, 16, 20, 23, 26, 30, 32, 37, 40, 42, 43, 53, 55, 58	0 to 48
III	Stereotypic Behavior	6, 11, 17, 27, 35, 45, 49	0 to 21
IV	Hyperactivity Noncompliance	1, 7, 13, 15, 18, 21, 24, 28, 31, 38, 39, 44, 48, 51, 54, 56	0 to 48
V	Inappropriate Speech	9, 22, 33, 46	0 to 12

Additionally, the ABC-C irritability subscale was used as criteria in order for patients to be eligible to participate in Period 2. Patients had to have a >35% irritability improvement in change from baseline to end of Period 1, in order to participate in the 6-month extension (Period 2).

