7.7.8. Children’s Sleep Habit Questionnaire (CSHQ)

The Children’s Sleep Habit Questionnaire will be completed by the parent/caregiver at Screening Visit 4, and Visit 7 EOS/ET. The parent/caregiver will complete a questionnaire comprised of 33 questions about their child’s sleep habits and possible difficulties with sleep. They will be asked to think about the past week in your child’s life when answering the questions. If last week was unusual for a specific reason (such as their child had an ear infection and did not sleep well or the TV set was broken), they will choose the most recent typical week. They will:

- Answer USUALLY if something occurs 5 or more times in a week.
- Answer SOMETIMES if it occurs 2-4 times in a week.
- Answer RARELY if something occurs never or 1 time during a week.

Parent/caregiver will also indicate whether or not the sleep habit is a problem by circling “Yes”, “No,” or “not applicable (N/A)”.

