- Patients who weigh ≤ 35 kg receiving a total daily dose of 250 mg CBD may increase to a daily dose of 500 mg.
Patients who weigh > 35 kg receiving a daily dose of 500 mg CBD may increase the dose to 750 mg/day.

The following questionnaires and scales will be administered at Visit 2, Visit 3, Visit 4, Visit 5, Visit 6, and Visit 7 EOS/ET, unless an exception is noted:

- ABC-C
- CGI-S
- Clinical Global Impression-Improvement (CGI-I) (not completed on Visit 2, Day 1)
- ADAMS
- C-SSRS
- Qualitative Caregiver Reported Behavioral Problems Survey (not completed at Visit 2)
- Children's Sleep Habit Questionnaire (Visit 4 and Visit 7 EOS/ET only)
- PARS-R

End of Study (EOS) / Early Termination Visit (ET):

Patients not on AEDs who are prematurely discontinued or do not qualify for Period 2, will complete the early termination procedures at Visit 4 EOS/ET.

Patients taking valproate or valproic acid for the treatment of seizures or epilepsy, including patients who prematurely discontinue, will taper their current study dose in the following manner beginning at Visit 7 EOS/ET. Should patients taking AEDs at the EOS continue to receive drug through Special Access (if available) they will not taper their dose.

- Participants who weigh 35 kg or less and were receiving 250 mg daily dose of ZYN002, will be reduced to 125 mg daily dose over one week. Only one sachet will be applied each day around the same time in the evening. After the taper, the participants will discontinue from the study at Week 40.
 - If the participant's dose was increased at Week 6 to 500 mg daily dose of ZYN002, the dose will be reduced to 250 mg daily dose over one week with 2 sachets applied each day around the same time in the evening. After the taper, the participants will discontinue from the study at Week 40.

- Participants who weigh 35 kg or more and were receiving 500 mg daily dose of ZYN002, will be reduced over two weeks. During the first week the dose will be reduced to 125 mg two times a day (applied 12 hours apart) which will make the total daily dose 250 mg. This is one sachet in the morning and one sachet in the evening. During the second week, the dose will decrease to 125 mg daily dose, which means one sachet each day for a week applied each day around the same time in the evening. After the taper, the participants will discontinue from the study at Week 41.

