4. STUDY DESIGN

This is an open-label study to assess the safety, tolerability and efficacy of CBD administered as ZYN002, a transdermal gel, for the treatment of child and adolescent patients with 22q. Male and female patients with 22q will be treated in Period 1 for 14 weeks.

Patients with less than a 25% improvement from baseline in the ABC-C Irritability subscale may have their total dose increased by the investigator at Week 6.

Patients that have made a $\geq 35\%$ improvement on the ABC-C Irritability sub-scale will be allowed to continue to Period 2 for an additional 24 weeks of treatment. Only patients taking AED medications for treatment of seizures or epilepsy will have an additional one or two-week Taper Period.

Approximately 20 male and female patients, ages 4 to < 18 years, will receive ZYN002.

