6.7.5. Children's Sleep Habit Questionnaire (CSHQ)

CSHQ will be evaluated for the change from Baseline to Week 38 (EOS/ET). The Children's Sleep Habit Questionnaire will be completed by the parent/caregiver at Screening and Visit 7 EOS/ET. The parent/caregiver will complete a questionnaire comprised of 33 questions about their child's sleep habits and possible difficulties with sleep. They will be asked to think about the past week in your child's life when answering the questions. If last week was unusual for a specific reason (such as their child had an ear infection and did not sleep well or the TV set was broken), they will choose the most recent typical week. They will:

- Answer USUALLY if something occurs 5 or more times in a week.
- Answer SOMETIMES if it occurs 2-4 times in a week.
- Answer RARELY if something occurs never or 1 time during a week.

Parent/caregiver will also indicate whether or not the sleep habit is a problem by circling "Yes", "No," or "not applicable (N/A)". A listing by patient of the questionnaire responses will be prepared along with a summary of change from baseline to EOS/ET.
Pharmacokinetic (PK) Analysis Set.

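### Week 22, 30 and 38 changes are tested against baseline only in patients selected at Week 14 for irritability improvement from that same baseline, so some improvement is expected even with no drug effect

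*SAP*

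**What the plan says.** **Analysis.** SAP 6.7.1 calls for "Change and percent change from Baseline to Weeks 6, 14, 22, 30 and 38/ET in the ABC-C subscales" and adds that "a t-test will be used to test if within treatment changes from baseline are different from 0". It also says: "Responder analyses (25% and 35% improvement) from baseline to each visit in each subscale will be calculated". SAP 6.7.2 repeats the change score and t-test for CGI-S at the same visits. SAP Section 11 puts all five visits in one table on the mITT set (Tables 14.2.1, 14.2.2 and 14.2.4). Under SAP 6.4.2 a patient needs only one post-baseline efficacy assessment to be in mITT.

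**Gate.** SAP 4 says that only patients with a 35% or greater "improvement on the ABC-C Irritability sub-scale will be allowed to continue to Period 2 for an additional 24 weeks of treatment". SAP 6.7.1 puts it slightly differently: "Patients had to have a >35% irritability improvement in change from baseline to end of Period 1". Footnote a to the Period 1 schedule (Protocol Table 5, SAP Table 4) gives everyone else an End of Study visit at Week 14.

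**Baseline.** SAP 6.6 and Protocol 13.3 define one baseline, the last assessment before first dose. It serves both the gate and every later change score.

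**End-of-study values.** The SAP synopsis says that patients not on AEDs who stop early or do not qualify for Period 2 "will complete the early termination procedures at Visit 4 EOS/ET". SAP 5.2 also treats Period 1 exits as Week 14/ET. Protocol 7.6.15.3 and 7.8, however, place every patient's EOS/ET visit at Week 38.

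**Sleep (CSHQ).** SAP 6.7.5 says "CSHQ will be evaluated for the change from Baseline to Week 38 (EOS/ET" and names only Screening and Visit 7 as collection points. Protocol 7.7.8 says the questionnaire "will be completed by the parent/caregiver at Screening Visit 4, and Visit 7 EOS/ET", and SAP Table 2 also schedules it at Week 14.

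**The concern.** A patient passes the gate more easily if the baseline irritability score was high by chance, or the Week 14 score low by chance. The Week 14 error is gone by Week 22. The baseline error is not, because every later change is measured from that same baseline. The mean change in continuers is therefore shifted towards improvement whatever the drug does.

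There is no control arm to expose the shift, no rule for patients without data at a visit, and no label saying that the later columns hold a selected subset. A reader comparing Week 14 with Week 38 in one mITT table could take a change of population for sustained benefit. SAP 6.7 leaves the choice of the most clinically meaningful efficacy result to be guided by the data, so the later columns could end up as the headline.

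**Working it through.** **Inputs from the documents.** N = 20 (SAP 4.2.1); irritability range 0 to 45 (SAP Table 6); gate 35%; one shared baseline; no control arm. The plan gives no SD, correlation, alpha or power, so it has no figure of its own to reproduce.

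**Assumptions.** Baseline mean/SD of 15/8, 20/9 and 25/8; between-visit correlation r of 0.6, 0.7 and 0.8, the same for all pairs of visits; two-sided 5% test; no change in any patient's true score.

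**Step 1: the sign, by algebra.** Write baseline as B = T + e0, Week 14 as T + e14 and Week 38 as T + e38, with independent errors of equal variance. The gate (B - W14)/B >= 0.35 is the same as 0.65·B - W14 >= 0, so the errors enter it with weights 0.65 (e0) and -1 (e14). Among those who pass:
- mean change at Week 14 = E(e14) - E(e0), proportional to -(1 + 0.65)
- mean change at Week 38 = -E(e0), proportional to -0.65

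About 0.65/1.65 = 39% of the chance improvement seen at Week 14 should therefore persist at each later visit.

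**Step 2: the size, by simulation.** 20,000 trials of 20 patients per row; gamma true scores plus normal visit error, rounded and bounded at 0 and 45; one-sample t-test on change to Week 38 in those who passed, run when at least three did.

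| Mean/SD | r | Pass gate | Trials with >=3 continuers | Week 14 change, continuers | Week 38 change, continuers | Rejects, given >=3 | Rejects, all trials |
|---|---|---|---|---|---|---|---|
| 15/8 | 0.6 | 20.6% | 81.6% | -9.03 | -3.63 | 14.8% | 12.1% |
| 15/8 | 0.7 | 18.0% | 72.7% | -8.14 | -3.27 | 14.2% | 10.3% |
| 15/8 | 0.8 | 14.3% | 56.1% | -6.99 | -2.79 | 13.2% | 7.4% |
| 20/9 | 0.6 | 16.6% | 66.9% | -11.14 | -4.43 | 14.6% | 9.8% |
| 20/9 | 0.7 | 13.9% | 53.8% | -10.05 | -4.00 | 14.9% | 8.0% |
| 20/9 | 0.8 | 10.4% | 34.5% | -8.69 | -3.45 | 13.5% | 4.7% |
| 25/8 | 0.6 | 8.6% | 24.4% | -12.06 | -4.70 | 13.7% | 3.3% |
| 25/8 | 0.7 | 6.3% | 12.8% | -11.06 | -4.39 | 15.5% | 2.0% |
| 25/8 | 0.8 | 3.7% | 3.4% | -9.66 | -3.78 | 13.8% | 0.5% |

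The last column is the product of the two rates, for example 0.816 × 0.148 = 0.121. The retained share agrees with Step 1: 3.27/8.14 = 0.40. In all 20 patients the mean change is 0.0, and the test rejects in about 5% of trials at Week 14, and also at Week 38 had everyone been followed. At least 98% of the continuers' rejections favour the drug.

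**Step 3: other assumptions.** Over 18 scenarios with r from 0.5 to 0.8, constant or decaying with time, the null mean change in continuers was -2.8 to -9.4 points at Week 22 and -2.8 to -5.5 at Week 38. It was an improvement in all 18.

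**Step 4: with a real effect.** At 15/8 and r = 0.7, a uniform 20% true improvement is 0.20 × 15 = 3.0 points. Continuers show -5.3 at Week 38.

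**Step 5: other scales.** For another subscale correlated 0.5 with irritability, the null mean change was -1.4 to -4.6 points, and the test declared benefit in 2% to 10% of trials, against 2.5% nominal in that direction.

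**Step 6: responder rates.** At 15/8 and r = 0.7, the null 35% responder rate at Week 38 is 36% of continuers, 18% if everyone were followed, and 6.5% if responding continuers are divided by all 20. Whether selection raises or lowers the rate depends on the denominator.

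**The case against.** The primary objective is safety. SAP 6.7 heads the efficacy section exploratory, names no primary efficacy endpoint and takes change to Week 14 as the first step. The gate is stated in the same section as the test, disposition will report how many patients entered the extension, and each summary shows n. No decision rule uses a Week 22 to 38 p-value. All of this stands, and it lowers the severity. It does not remove the bias or label the columns.

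Four stronger readings are tempting, and the documents do not support them:

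- *The later t-tests will come out positive whatever the drug does.* The shift is in the expected mean. About 85% of null trials with at least three continuers do not reject, and few patients may pass by chance.
- *The later responder rates are inflated.* SAP 6.7.1 states no denominator. With all mITT patients in the denominator, selection lowers the rates. The defect is the missing definition.
- *Week 38/ET pools every early exit.* The SAP synopsis and SAP 5.2 place Period 1 exits at Visit 4 or Week 14; Protocol 7.6.15.3 and 7.8 say otherwise. What can be said is that the passages conflict.
- *The Week 14 sleep data are discarded.* SAP 6.7.5 also mentions change to EOS/ET, and EOS is Week 14 for non-qualifiers, so their values may be included. No Week 14 analysis of the whole cohort is planned, however.

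**Conclusion.** The point holds for the mean change and the t-test on irritability. Week 22 and 30 results, and Week 38 results subject to how EOS/ET values are assigned, describe patients selected at Week 14 on the variable being tested and against the same baseline. The direction follows from the design. The size rests on the assumed means, SDs and correlations, none of which the documents supply.

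The other ABC-C subscales and CGI-S are affected only as far as they correlate with irritability. Weeks 6 and 14 in the full mITT set are free of this selection, though still uncontrolled. Because efficacy is exploratory, this should be fixed but does not threaten the trial's primary purpose.

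**What to change.** 1. Limit t-tests against baseline to Weeks 6 and 14 in the full mITT set.
2. Title the Week 22 to 38 tables *Week 14 irritability responders who continued*, make them descriptive only, and show the same patients' Week 14 values and change from Week 14. That second comparison is biased the other way (at 15/8 and r = 0.7 under no effect, -3.27 + 8.14 = +4.87 points), so it should carry no test either.
3. State the responder denominator, giving n observed and n mITT at each visit. If non-continuers are counted as non-responders, do so only for the irritability 35% threshold, label it a composite, and do not make it the sole presentation. A patient with 30% irritability improvement meets the 25% threshold yet cannot continue, and one who improved on another subscale may also be barred.
4. Reconcile the Period 1 schedule footnote, the SAP synopsis and SAP 5.2 with Protocol 7.6.15.3 and 7.8, so that Week 14 exits are not placed in Week 38. Assign early-termination values by actual study day. Also reconcile the two wordings of the gate, and the responder thresholds (25% and 35% in SAP 6.7.1, 25% and 50% in Table 14.2.2).
5. Add CSHQ change from baseline to Week 14 in all mITT patients.

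The cost is wording, table titles, one reference column and one sleep summary, with no new data. The Note to File says the SAP will not be updated, so the changes can be made in the table titles and the study report. The downside for the sponsor is that the long-term results will look less favourable.

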6.7.1. Autism Diagnostic Observation Schedule® (ADOS®-2)

The ADOS (Western Psychological Services) is a semi-structured assessment of communication, social interaction and play or imaginative use of materials for individuals suspected of having 22q or other pervasive developmental disorders from 12 months through adulthood (Lord et al. 2000). The ADOS®-2 will be completed at Screening. The comparison score will be used to determine the level of 22q related symptoms as follows:

Low = 1 to 4 - no worse than mild autism symptoms
Moderate = 5 to 7 - moderate autism symptoms
High = 8 to 10 - high level of autism symptoms

6.7.2. Clinical Global Impression – Improvement, Severity Scales

The Clinical Global Impression Scales, Severity and Improvement, are commonly used in clinical trials (Leigh et al. 2013) as they allow the clinician to utilize the history from the caregiver and incorporate the score into a clinical rating for the severity of symptoms.

CGI-S is a 7-point scale that requires the clinician to rate the severity of the patient's illness at the time of assessment, relative to the clinician's past experience with patients who have the same diagnosis. Considering total clinical experience, a patient is assessed on severity of mental

illness ([Table 7](#)). CGI-S will be assessed at Screening, Visit 2, Visit 3, Visit 4, Visit 5, Visit 6, and Visit 7 EOS/ET to judge the severity of the symptoms of 22q. Change and percent change from Baseline to Weeks 6, 14, 22, 30 and 38/ET in the CGI-S score will be calculated. In addition, a t-test will be used to test if within treatment changes from baseline are different from '0'.

Table 7: Clinician Global Impression-Severity (CGI-S) Scale

Considering your total clinical experience with this particular population, how mentally ill is the subject at this time?	
Score	Description
1	Normal, not at all ill
2	Borderline mentally ill
3	Mildly ill
4	Moderately ill
5	Markedly ill
6	Severely ill
7	Among the most extremely ill

CGI-I is a 7-point scale that requires the clinician to assess how much the patient's illness has improved or worsened relative to a Baseline state at the beginning of the intervention and rated as: 1 - very much improved; 2 - much improved; 3 - minimally improved; 4 - no change; 5 - minimally worse; 6 - much worse; or 7 - very much worse. Information from both the clinician and the parent/caregiver history are incorporated into a clinical rating. CGI-I will be assessed at Visit 3, Visit 4, Visit 5, Visit 6 and Visit 7/EOS/ET. A summary of counts and percentages for each category will be tabulated at each post baseline visit. In addition, a shift table from baseline to each post baseline visit will be produced [Table 8](#):

Table 8: Clinician Global Impression - Improvement (CGI-I) Scale

Rate total improvement whether or not, in your judgement, it is due entirely to study drug.		
Compared to his condition at admission to the project, how much has he changed?		
Score	Description	Category
1	Very much improved	Improved
2	Much improved	Improved
3	Minimally improved	Not improved
4	No change	Not improved
5	Minimally worse	Not Improved
6	Much worse	Not improved
7	Very much worse	Not Improved

6.7.3. Columbia Suicide Severity Rating Scale (Children's Version)

The C-SSRS (Children's version) is to be completed at Screening and all study visits including Unscheduled Visits. The C-SSRS assessment will be conducted only if the patients are of an

appropriate age (6 years or older) and capable of understanding and answering the questions in the Investigator's opinion. For patients under the age of 6 or who are not capable of understanding and answering the questions in the Investigator's opinion, the Investigator will consider the trend in ABC-C Irritability when assessing the risk of self-harm for an individual patient. Patient counts and percentages will be summarized for the C-SSRS.

6.7.4. Qualitative Caregiver Behavioral Problems Survey

At the Screening Visit, the parent/caregiver will be asked the following question "What are the three behavioral, emotional, or social problems that most impacted your son/daughter and his/her family in approximately the past year?" At Visit 3, Visit 4, Visit 5, Visit 6, and Visit 7 EOS/ET the parent/caregiver will be reminded of their responses at the Screening Visit in order to rate the three questions for improvement or worsening. A listing will be prepared for the open text responses for the final analysis.

6.7.5. Children's Sleep Habit Questionnaire (CSHQ)

CSHQ will be evaluated for the change from Baseline to Week 38 (EOS/ET). The Children's Sleep Habit Questionnaire will be completed by the parent/caregiver at Screening and Visit 7 EOS/ET. The parent/caregiver will complete a questionnaire comprised of 33 questions about their child's sleep habits and possible difficulties with sleep. They will be asked to think about the past week in your child's life when answering the questions. If last week was unusual for a specific reason (such as their child had an ear infection and did not sleep well or the TV set was broken), they will choose the most recent typical week. They will:

- Answer USUALLY if something occurs 5 or more times in a week.
- Answer SOMETIMES if it occurs 2-4 times in a week.
- Answer RARELY if something occurs never or 1 time during a week.

Parent/caregiver will also indicate whether or not the sleep habit is a problem by circling "Yes", "No," or "not applicable (N/A)". A listing by patient of the questionnaire responses will be prepared along with a summary of change from baseline to EOS/ET.
Pharmacokinetic (PK) Analysis Set.

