11.1. Individual Patient Data Listings

Listing Number	Title	Population
16.1	Listing of Patient Disposition	Enrolled
16.2	Listing of Demographics	Enrolled
16.3	Listing of Baseline Characteristics	Enrolled
16.4	Listing of Medical History	Enrolled
16.5.1	Listing of Prior/Concomitant Medications	Enrolled
16.5.2	Listing of Anti-Epileptic Drugs	Enrolled
16.6.1	Listing of Physical Exam Results	Enrolled
16.6.2	Listing of Neurological Exam Results	Enrolled
16.7	Listing of Protocol Deviations	Enrolled
16.8	Listing of Inclusion and Exclusion	Enrolled
16.9.1	Listing of Urine Drug Screen	Enrolled
16.9.2	Listing of Serum/Urine Pregnancy Results (Female Patients Only)	Enrolled
16.10	Listing of Vital Signs	Enrolled
16.11	Listing of 12-Lead ECG	Enrolled
16.12.1	Listing of Skin Assessment Examination	Enrolled
16.12.2	Listing of Skin Irritation Examination	Enrolled
16.13	Listing of Study Drug Application Record	Enrolled
16.14.1	Listing of Chemistry Labs	Enrolled
16.14.2	Listing of Hematology Labs	Enrolled
16.14.3	Listing of Urinalysis Labs	Enrolled
16.15	Listing of Testosterone Labs (Male Patients Only)	Enrolled
16.16	Listing of Columbia Suicide Severity Rating Scale (CSSRS-Children)	Enrolled
16.17	Listing of Pharmacokinetic Blood Sample Collection Record	Enrolled
16.18.1	Listing of Adverse Events	Enrolled
16.18.2	Listing of Deaths	Enrolled
16.18.3	Listing of Serious Adverse Events	Enrolled
16.18.4	Listing of Adverse Events Leading to Discontinuation	Enrolled
16.18.5	Listing of Patient Skin Irritation from Diary	Enrolled
16.20	Listing of Qualitative Caregiver Reported Behavioral Problems Survey	Enrolled
16.21	Listing of Children's Sleep Habit Questionnaire	Enrolled
16.22	Listing of ABC-C Checklist	Enrolled
16.23	Listing of CGI-S Scale	Enrolled
16.24	Listing of CGI-I Scale	Enrolled
16.25	Listing of PARS-R	Enrolled
16.26	Listing of ADAMS Scale	Enrolled
16.27	Listing of C-SSRS	Enrolled
16.28	Listing of AED Blood Sample	Enrolled

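### SAP 6.7.5 plans no Week 14 summary of the sleep questionnaire, the only post-baseline point scheduled for every patient, and its Week 38 (EOS/ET) target can be read in two ways

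*SAP*

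**What the plan says.** **Collection.** Protocol 7.7.8 says the questionnaire "will be completed by the parent/caregiver at Screening Visit 4, and Visit 7 EOS/ET". The SAP synopsis, in its list of scales given during treatment, has "Sleep Habit Questionnaire (Visit 4 and Visit 7 EOS/ET only". SAP Table 2 marks Screening, Week 14, Week 38 and ET, and the Period 1 schedule (SAP Table 4, protocol Table 5) marks Week 14.

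**Analysis.** SAP 6.7.5 says the questionnaire "will be completed by the parent/caregiver at Screening and Visit 7 EOS/ET", with no Visit 4. It plans only one change from baseline: "CSHQ will be evaluated for the change from Baseline to Week 38 (EOS/ET". On output it says: "A listing by patient of the questionnaire responses will be prepared along with a summary of change from baseline to EOS/ET".

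**Displays.** The efficacy tables in SAP Section 11 (14.2.1 to 14.2.6.2) cover the ABC-C, ADAMS, CGI-S, CGI-I and PARS-R. For the CSHQ there is only Listing 16.21, "Listing of Children's Sleep Habit Questionnaire". The interim scales in SAP 5.1 are the ABC-C, ADAMS, CGI and PARS-R. SAP Section 10 records no changes from the protocol.

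**Who is seen when.** Footnote a of the Period 1 schedule gives every patient a Week 14/ET visit and makes it the end-of-study visit for patients who do not qualify for Period 2. SAP Section 4 admits to Period 2 only patients with at least 35% improvement in ABC-C Irritability.

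**The concern.** A scale given at two post-baseline visits is planned for summary at the later one only, and the patients who reach that visit have been selected on their behavioural response. Sleep and irritability may well move together in these children, so a Week 38 mean could look better than the effect in the treated group as a whole. It would also rest on fewer patients.

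The label does not settle who is counted. EOS/ET is a Week 14 visit for some patients and a Week 38 visit for others, so two programmers could produce different tables from 6.7.5. Under neither reading would the sleep result stand beside the Week 14 results of the other scales, although SAP 6.7 puts change to the end of Period 1 first in the efficacy analysis.

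**Working it through.** The plan gives no CSHQ effect, SD, power or expected continuation rate, so there is no figure to reproduce. The check compares the texts and then illustrates the size under stated assumptions.

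**Step 1. Visits scheduled against visits analysed**

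| Source | Screening | Week 14 | Week 38 |
|---|---|---|---|
| Protocol 7.7.8 | yes | yes | yes |
| SAP Table 2 | yes | yes | yes (ET also marked) |
| SAP 6.7.5, visit list | yes | **no** | yes |
| SAP 6.7.5, change from baseline | baseline | **no** | yes (EOS/ET) |
| SAP Section 11, summary table | none | none | none |

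The CSHQ is not given on Day 1, so under SAP 6.1.2 its baseline is the Screening value.

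**Step 2. What Week 38 (EOS/ET) can mean**

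- *Visit 7 only.* Contributors are mainly patients who passed the gate. I say mainly because protocol 7.8 also sends early discontinuations to a visit labelled Visit 7 EOS/ET. Protocol 7.6.15.3 and 7.8 place the end-of-study visit at Week 38.
- *Each patient's own EOS/ET visit.* The synopsis has non-qualifiers complete these procedures at Visit 4. SAP 6.1.4 defines the end-of-treatment value as the last post-baseline value, although 6.7.5 does not refer to it. Up to all 20 patients then contribute.

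**Step 3. Size under the Visit 7 reading**

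Assumptions: 20 patients (the planned number), no dropout, a share p of 30%, 50% or 70% passing the gate, and the same SD at both visits. None of these shares is in the documents.

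- Patients at Week 38: n = 20p.
- 95% CI half-width in SD units: t(0.975, n−1)/√n. At Week 14 with n = 20 this is 2.093/4.472 = 0.47.
- Shift in mean change from selection, in SD units: ρ·φ(z)/p, where z is the normal cut-off exceeded by a share p and ρ is the correlation between CSHQ change and irritability improvement (assumed 0.3 to 0.5, bivariate normal).

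| Share passing | n at Week 38 | Half-width (SD) | Shift, ρ = 0.3 to 0.5 (SD) |
|---|---|---|---|
| 30% | 6 | 2.571/√6 = 1.05 | 0.35 to 0.58 |
| 50% | 10 | 2.262/√10 = 0.72 | 0.24 to 0.40 |
| 70% | 14 | 2.160/√14 = 0.58 | 0.15 to 0.25 |

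With 20% dropout before Week 14, there are 16 patients at Week 14 (half-width 0.53) and 5, 8 or 11 at Week 38 (1.24, 0.84 or 0.67).

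**Step 4. The other reading**

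If k patients qualify and all 20 contribute, the pooled mean is

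[k × (Week 38 mean change in qualifiers) + (20 − k) × (Week 14 mean change in non-qualifiers)] / 20.

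The sample size is no longer the problem. The quantity is neither the Week 14 change in all patients nor the Week 38 change in those who continued, and time on treatment is tied to response status.

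**The case against.** Several points on the other side are sound.

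- **Week 14 is in scope elsewhere.** The SAP synopsis says that all efficacy assessments are summarised at Weeks 6, 14, 22, 30 and 38, and SAP 6.7 puts change to Week 14 first. This makes the defect look like an inconsistency and not a decision. It does not cure it: the synopsis line is generic (the CSHQ is not given at Weeks 6, 22 or 30), and no table delivers a Week 14 result.
- **It may be a faulty visit list.** The PARS-R paragraph in SAP 6.7.6 omits Week 6, which SAP Tables 2 and 4 schedule. That omission is also in protocol 7.7.9, whereas for the CSHQ protocol 7.7.8 does include Visit 4. A drafting slip is plausible, but the text still needs correcting.
- **The data are not lost.** A reader might infer that the Week 14 responses are discarded. They are not: 6.7.5 and Listing 16.21 present responses by patient. A listing of answers to 33 questions is not a summary of change, however.
- **Responder-only is not established.** A reader might infer that the table will show responders only. That holds only if EOS/ET means Visit 7 strictly, and the documents support the other reading too. The precision loss in Step 3 and the mixing in Step 4 are alternatives and do not add up.
- **The stakes are small.** The primary objective is safety and tolerability, no primary efficacy endpoint was chosen, and the CSHQ is one of several exploratory scales. Leaving it out of the interim scales is a legitimate scoping choice. This point stands in full.

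**Conclusion.** The point holds as a gap and an ambiguity in SAP 6.7.5. The section omits a scheduled visit, in conflict with protocol 7.7.8 and SAP Tables 2 and 4. It specifies no summary at the only post-baseline CSHQ point scheduled for all patients, and it leaves its one target open to two readings. Neither reading gives a clean result: one is selected by the Period 2 gate and the other pools two time points. The promised summary also has no table.

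The figures in the working apply only to the strict Visit 7 reading and rest on assumed pass rates, correlations and equal SDs. They show the order of magnitude and do not predict the result. The documents do not support calling the Week 38 patients a hand-picked minority: entry follows a written rule, and at a 70% pass rate they would be 14 of 20.

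Severity is low, because the SAP attaches no test, threshold or decision to the CSHQ.

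**What to change.** In SAP 6.7.5:

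1. Restore Visit 4 to the visit list.
2. Summarise change from Baseline (Screening) to Week 14 in the mITT set.
3. Report Week 38 separately, labelled as Period 2 patients only.
4. State how ET values are assigned, so that Week 14 and Week 38 values are not pooled in one column.

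In SAP Section 11, add a numbered CSHQ summary table. A 95% CI and inclusion in the Period 1 displays would help but are optional in a descriptive plan.

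The cost is one paragraph and one table, with no new data. The Note to File says that the protocol and SAP will not be updated. If that stands, a labelled additional table with a documented reason does the same job.
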